1.5.10 Adverse/Outcome Events

Most symptoms, signs and clinical events will be captured by questionnaire during routine scheduled clinic and telephone visits. Data collection forms are specifically designed to capture known adverse events from the LifeVest including physical discomfort (rash, etc.). Inappropriate shock events will be adjudicated, as above. Site investigators will make a determination for all deaths and hospitalizations about whether the event was related to participation in the study; all such events will be adjudicated and summarized for the Data Safety Monitoring Board (DSMB).

1.5.11 Analysis Plan for VEST

Treatment effects on the primary outcome, sudden death and death due to ventricular arrhythmia, will be assessed using stratified exact methods to compare cumulative incidence in the VEST and control groups at 60/90 days. An exact test of the primary null hypothesis of no treatment effect will be conducted using a two-sided alpha of 5%. This analysis will be by intention to treat (ITT), without regard to adherence to the assigned study intervention or other aspects of care. The analysis will be jointly

OUTCOMES	PRIMARY/S ECONDARY	DATA SOURCE	ADJUDICATED
Sudden death mortality	Primary	Records/interviews [†]	Yes
All-cause (total) mortality	Secondary	Records/interviews [†]	Yes

VEST	Protocol	1	
Cause-specific mortality			
Non-sudden death	Secondary	Records/interviews [†]	Yes
Ventricular Arrhythmia Death	Primary	Records/interviews [†]	Yes
Other Fatal Arrhythmia	Secondary	Records/interviews [†]	
Non-Sudden Fatal MI	Secondary	Records/interviews [†]	Yes
Fatal Congestive Heart Failure	Secondary	Records/interviews [†]	Yes
Other Cardiac Death	Secondary	Records/interviews [†]	Yes
Fatal Stroke	Secondary	Records/interviews [†]	Yes
Other Non-cardiac Death	Secondary	Records/interviews [†]	Yes
Indeterminate Cause of Death	Secondary	Records/interviews [†]	Yes
Time to death after 1 st VT/VF episode	Secondary	Records/ICD/Reveal	Yes
Non-Fatal Cardiovascular Events			
MI	Secondary	Records/interviews [†]	Yes
Atrial fibrillation	Secondary	Records/interviews [†] / ICD/Reveal	Yes
Congestive heart failure	Secondary	Records/interviews [†]	Yes
Stroke	Secondary	Records/interviews [†]	Yes
LifeVest Events			
Ventricular Tachyarrhythmia	Secondary	LifeVest	Yes
LifeVest Shocks delivered	Secondary	LifeVest	Yes
30 Beats of VT (CL 330-370 msec)	Secondary	LifeVest	Yes
Inappropriate Shock - SVT	Secondary	LifeVest	Yes
Inappropriate Shock - Malfunction	Secondary	LifeVest	Yes
Time to 1 st episode of VT/VF	Secondary	LifeVest	Yes
Adverse Events	-		
Device-attributable Death or Hospitalization	Secondary	Records/interviews [†]	Yes
Device-related Symptom or Sign	Secondary	Data Form	No
Device Change-out	NA	Data Form	No
Other Adverse Event	Secondary	Data Form	No
Vest Compliance	Secondary	LifeVest	
ICD Implantation	Secondary	Data Form	No
Quality of Life	Secondary	QOL Instruments	No
Resource Utilization/Cost	Secondary	Data form	No

+ - Includes information from medical records, death certificates, interviews of next-of-kin or personal physicians, and National Death Index searches

VF - Ventricular fibrillation; VT - Ventricular tachycardia; SVT - Supraventricular tachycardia; ICD - Implantable cardioverter defibrillator

stratified by length of follow-up period (to account for the higher expected rate in patients with 90 day follow-up), and randomization stratum, as jointly defined by EF and receipt of PCI and/or CABG during the hospitalization for the index MI.

We will also conduct a secondary "modified intention-to-treat" analysis of sudden death and death due to ventricular arrhythmia, total mortality, and other secondary outcomes. For this analysis, follow-up time will start at the time of discharge instead of randomization, and end 60/90 days after discharge, and participants who are randomized but die before discharge from the index hospitalization will be excluded. For death outcomes, this analysis will use the stratified exact methods specified for the primary analysis; for more common secondary outcomes, asymptotic methods will be considered.

We will also analyze treatment effects on overall mortality and non-sudden death, non-fatal cardiovascular events, ventricular arrhythmias, adverse events, LifeVest compliance, ICD implantation, quality of life and resource utilization/cost. For rare outcomes, exact methods will be used, as for the primary endpoint. For VEST therapies and hospitalizations, we will use the Anderson-Gill extension of the Cox model for repeated events, with robust standard errors, to better capture information from high-risk participants with repeated VEST therapies or hospitalizations.

We will also conduct a secondary, "as treated" analysis of sudden death and death due to ventricular arrhythmia, total mortality, and other secondary outcomes. The primary ITT analysis will estimate effectiveness of the vest, averaged over variations in compliance. We will attempt to estimate the efficacy of the vest for prevention of sudden death and death due to ventricular arrhythmia as well as total mortality using survival models treating observed vest use as a time-dependent covariate. For sudden death and death due to ventricular arrhythmia, we will

6

Protocol

use a Fine-Gray model treating other deaths as competing risks; a standard Cox model will be used for total mortality.

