1.5.2 Study Participants

Participants hospitalized with an MI (or discharged after a recent MI) will be approached and evaluated for enrollment in the study. A standard definition of acute MI based on recently published criteria will be used:1

> • Detection of rise and/or fall of cardiac biomarkers (preferably troponin) with at least one value

Table 1 VEST inclusion and exclusion criteria

	Table 1. VEST inclusion and exclusion	n crit	ieria.
	INCLUSION CRITERIA		EXCLUSION CRITERIA
	1. Patients identified in the hospital	1.	Existing ICD or indication for an
	or within 7 days after discharge		ICD at the time of screening
	with a diagnosis of an acute MI	2.	Existing unipolar
	(STEMI or Non-STEMI) ¹		pacemakers/leads
1	LV ejection fraction ≤35%,	3.	Chronic renal failure requiring
	determined at the following time		hemodialysis after hospital
	point:		discharge
	a) if no PCI within the first 8	4.	Chest circumference too small or
	hours following the MI:		too large for LifeVest garment*
	≥8° after MI	5.	Participants discharged to a
	b) if acute PCI occurs within 8°		skilled nursing facility with an
	of MI: ≥8° after PCI	_	anticipated stay > 7 days
	c) if CABG is planned (before		Pregnancy
ŀ	or within 7 days of		Inability to consent
-	discharge), wait to enroll	8.	Any other condition or
	and then use the most		circumstance that in the
	recent assessment at		judgment of the clinician makes
	least 48° post CABG.		the participant unsuitable for the
	3. Age > 18 years		study
		1	

*as of this writing, garments are available for chest circumference of 26-56 inches.

above the upper limit of normal (ULN) for the particular lab, together with evidence of myocardial ischemia with at least one of the following:

- Symptoms of ischemia
- ECG changes indicative of new ischemia (new ST-T changes) or new left bundle branch block (LBBB);
- Development of pathological Q waves in the ECG
- Imaging evidence of new loss of viable myocardium or new regional wall motion abnormality.
- Detection of rise and/or fall of cardiac biomarkers (preferably troponin) with at least one value above 3 x ULN for your lab in the setting of a percutaneous coronary intervention (PCI).

Those who meet the inclusion criteria and do not meet any of the exclusion criteria will be eligible for randomization in VEST. Table 1 lists the specific inclusion and exclusion criteria for VEST.

[figure not shown]

Figure 1. Overview of study timeline

Protocol

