1.5.4 Schedule and Description of Participant Visits

Each of the study

participants will be first seen in the hospital during their admission for MI or after discharge in the clinic within the window of enrollment. They will then be followed with one phone call and one clinic visit. The schedule for testing and data collection is outlined in Table 2. The visit timeline and windows for visits are provided in Chapter 3 of the Operations Manual.

• *Enrollment Visit (V0):* Begins during the participant's hospitalization for MI
 Table 2: Scheduled visits and data collection

DATA COLLECTED AND		VISITS			
TESTING PERFORMED		Post-discharge			
	V0	V1	V2	Registry	
	Enrollment	1 Month Phone	3 Month Visit		
Screening and Medical History	Х				
Vital signs, discharge meds & diagnoses (from chart)	X				
Symptom Checklist		Х	Х		
Medication Review	Х	Х	Х		
Medical Care Utilization		Х	Х	Х	
Vital Status			Х	Х	
QOL Survey			Х		
Test Reports 12 lead ECG Local Labs 	From Medical Record				
Echocardiography	From Medical Record		From Medical Record	From Medical Record	
Home Monitoring LifeVest 	upload baseline at fitting		in 1 st week, 1 weekly		

or within the window of enrollment after discharge. Participants who meet enrollment criteria will be asked to participate in the study after they are medically stable. After consent for VEST, they will be enrolled and randomized to vest or no vest. If randomized to vest, they may leave the hospital with the vest. The enrollment visit will involve collection of information and data abstracted from the hospital chart.

- *1 Month Follow-up Telephone Call (V1)*: All participants will be contacted by phone to gather follow-up data. Participants will be asked about changes in medication, intervening hospitalization or visits to the emergency department, any problems with the vest (if randomized to the LifeVest) and a simple symptom checklist.
- *3 Month Visit (V2):* All participants will be seen for clinical data collection/final visit. Participants will be asked about changes in medication, intervening hospitalization or visits to the emergency department, any problems with the vest (if randomized to the LifeVest), and a simple symptom checklist. The patient's most recent EF will be extracted from his/her medical record and assessment of qualification for primary prevention ICD will also be recorded. A Quality of Life survey will be

Protocol

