1.5.9 Outcome Variables

The outcome measures are outlined in Table 3. The primary outcome is sudden death and death due to ventricular arrhythmia at 3 months (90 days) after randomization. We will use the following definition of Sudden Death:

For witnessed deaths, sudden cardiac death will be defined as an unexpected, non-traumatic, nonself-inflicted fatality in otherwise stable participants who die within one hour of the onset of the terminal symptoms. For persons dying more than one hour after a cardiac arrest from a ventricular arrhythmia, the Non-Sudden Death due to Ventricular Arrhythmia category should be used.

For unwitnessed deaths, participants will meet the definition of sudden death if they are found dead within 24 hours of being well, assuming there is no evidence of another cause of death during that time period. Device arrhythmia and autopsy results may be used when available. For unwitnessed deaths when the participant was found dead more than 24 hours after last being seen, no device arrhythmia data are available, no autopsy results are available and no other information is available regarding the cause of death, the Indeterminate category should be used.

We also include non-sudden deaths due to ventricular arrhythmia in the primary outcome definition. Deaths are categorized as such when a person suffers a cardiac arrest from an acute ventricular arrhythmia, is resuscitated and admitted to the intensive care unit, and then dies several days after the arrest from complications (e.g., neurological damage). Secondary outcomes for VEST are total mortality, non-sudden death and other cause-specific mortality (non-sudden fatal MI, other cardiac death, non-cardiac death, and indeterminate cause of death), hospitalization for MI, congestive heart failure, stroke/transient ischemic attack, ventricular arrhythmias, adverse events, LifeVest compliance, eventual ICD implantation, quality of life, and resource utilization/cost. The wearable defibrillator can do continuous ECG recording and monitor time worn. Therefore, data for several of the secondary outcomes that are analyzed within the intervention group will come from the LifeVest transmissions.

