1.5.12 Sample Size Calculations

When the trial was originally designed, the sample size for the VEST study was estimated to be 1,890. This assumed a power of 80%, with a 2-sided alpha of 0.05 and a 2:1 randomization scheme. The VEST sample size was carefully computed using data-based estimates of the following factors:

1. Mortality due to sudden death in the first 2 months following an MI in patients with $EF \le 35\%$ is 2.4%. The VALIANT Study, the EPHESUS Study, and the DINAMIT Study are three recent studies reporting on mortality and sudden death rates in the early period following an MI in populations similar to our study population. A meta-analysis of these three studies populations gives a summary estimate for sudden death rate of 2.4%.

2. Mortality due to sudden death in the first 3 months following an MI in patients with $EF \le 35\%$ is 3.0%. Using month-by-month data on sudden death in VALIANT, we estimate that extending follow-up from 2 to 3 months will increase the sudden death rate by 25%, from 2.4% to 3.0%. This accounts for declines in the sudden death rate in the weeks following MI.

3. Mortality due to ventricular arrhythmias in the first 3 months following an MI in patients with $EF \le 35\%$ is 2.73%. The wearable defibrillator vest will be effective at reducing only sudden death due to a ventricular arrhythmia. The preliminary data from the wearable defibrillation vest shows that 91% of all sudden cardiac arrests are due to ventricular arrhythmias. This is consistent with estimates in the literature. *Therefore*, 91% of 3.0% would give us an expected mortality of 2.73% due to ventricular arrhythmia.

4. The effectiveness of the wearable defibrillator to reduce sudden death due to ventricular arrhythmias will be 71.9%. Previous analyses show that the LifeVest conversion success rate is 98% for syncopal VT/VF. Based on early experience in VEST and planned changes in randomization procedures, we have targeted an intention-to-treat compliance rate with the LifeVest of 70%. This means that participants assigned to the LifeVest will wear it for 70% of all hours in the 3 months following randomization, including days when the LifeVest is not worn at all. However, since compliance and event rates are both anticipated to be highest in the earliest weeks of the trial we anticipate the LifeVest will be used during more than 70% of sudden death events. Thus, we estimate that the LifeVest will reduce sudden death due to syncopal VT/VF by 71.9%.

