2.6 STATISTICAL ANALYSIS AND DISSEMINATION

The DCC will be primarily responsible for statistical analysis of the research questions posed by VEST. The data will reside with the DCC and will be analyzed by DCC personnel for interim DSMB reports and for publications, presentations and other dissemination activities according to the plan described in section 1.5.11 and with scientific oversight by the Steering Committee.

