1. Modified intention to treat. We will omit from this analysis, patients who do not survive until discharge from the index hospitalization, and the 60/90 day follow-up will begin at the later event of randomization or discharge. The rationale is that the vest is essentially never worn in hospital, and so can provide no protection until after discharge. Although mortality is highest soon after a serious MI, close in-hospital monitoring is expected to keep the in- hospital death rate low. As part of this analysis, we will characterize times from randomization to discharge using histograms, stratified by group.

2. Adjustment for baseline imbalances. If we find substantial imbalances in powerful baseline prognostic variables with the potential to confound treatment assignment meaningfully, we will perform a sensitivity analysis using a logistic regression model to adjust for these factors. If more than two factors need to be adjusted for, we will summarize them using propensity scores [Rosenbaum 1983], then use a logistic model to adjust for the scores as a three-knot cubic spline, requiring two basis functions, so that the conservative rule of thumb of approximately 10 events per variable is observed [Vittinghoff 2006].

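### Protocol 1.5.11 starts the modified-ITT clock at discharge even for participants randomized after discharge; the SAP uses the later of the two dates, and the protocol should match it

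*Combined protocol and SAP*

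**What the plan says.** Protocol 1.5.11 defines a secondary modified-ITT analysis in which "follow-up time will start at the time of discharge instead of randomization, and end 60/90 days after discharge". It also states that "participants who are randomized but die before discharge from the index hospitalization will be excluded". It applies this analysis to the primary outcome, total mortality and other secondary outcomes.

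SAP B.1, item 1 describes the same analysis with the same exclusion, but "the 60/90 day follow-up will begin at the later event of randomization or discharge". Its stated reason is that the vest is essentially not worn in hospital and cannot protect before discharge. B.1 names no outcome beyond the primary one for this analysis.

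Enrollment after discharge is allowed. Table 1 in section 1.5.2 accepts patients identified in hospital "or within 7 days after discharge". Section 1.5.4 says participants are "first seen in the hospital during their admission for MI or after discharge in the clinic within the window of enrollment", with consent and randomization at that visit.

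The main analysis is anchored elsewhere. Section 1.5.9 states: "The primary outcome is sudden death and death due to ventricular arrhythmia at 3 months (90 days) after randomization".

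Section 2.6 has DSMB reports and publications analysed "according to the plan described in section 1.5.11". Neither document says which prevails if they differ.

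**The concern.** A participant must be alive to be randomized. If the clock starts at a discharge that came first, the days between the two dates are event-free by construction. Because the protocol also fixes the end at 60 or 90 days after discharge, those days are taken off the follow-up after randomization. Section 1.5.11 makes no provision for delayed entry; it compares cumulative incidence by exact methods.

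For example, take someone randomized 7 days after discharge who dies suddenly 86 days after randomization. The death counts in the primary ITT analysis. Under 1.5.11 it falls on day 93 after discharge, outside the modified-ITT window, although the participant stays in that analysis. Under the SAP rule it counts.

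Two analysts, each following one document, could therefore report different modified-ITT counts for the primary outcome. The protocol version would be labelled as a 60/90-day incidence without covering 60/90 days at risk.

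**Working it through.** **Inputs**
- Gap g from discharge to randomization: 0 to 7 days for post-discharge enrollees (Table 1, section 1.5.2).
- Sudden death: 2.4% at 2 months and 3.0% at 3 months (section 1.5.12, items 1 and 2).
- Design rates: 3.0% control and 1.02% LifeVest (section 1.5.12, item 5), a ratio of 0.34.
- Allocation 2:1; final size 2300 (section 1.5.12).
- Share enrolled after discharge: not in the documents, so a range is used.

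**The plan's own figures.** The documents give no figure for the modified-ITT analysis. The rates used here do check: 2.4% × 1.25 = 3.0%. The pooled two-proportion formula with continuity correction at 3.0% versus 1.02%, 80% power, two-sided 5% and 2:1 gives 623 controls, or 3 × 623 = 1869 in total, close to the stated 1890.

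**Step 1: time at risk after randomization.** The protocol rule gives 90 − g or 60 − g days; the SAP rule gives the full 90 or 60. At g = 7 the protocol rule leaves 83 of 90 days (7/90 = 7.8% lost) or 53 of 60 (7/60 = 11.7% lost).

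**Step 2: risk curve.** Assume F(t) = A(1 − e^(−kt)), with time zero at discharge. Set x = e^(−30k). Then F(90)/F(60) = (1 + x + x²)/(1 + x) = 1.25, so x² − 0.25x − 0.25 = 0 and x = 0.6404. Hence k = 0.01486 per day and A = 2.4%/(1 − x²) = 4.07%. The protocol's rates run from the MI, so putting time zero at discharge is an approximation.

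**Step 3: counted events for a control participant with gap g.** With follow-up length T, the protocol counts F(T) − F(g) and the SAP counts F(T + g) − F(g).

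| T (days) | g (days) | Protocol, per 100 | SAP, per 100 | Fewer under protocol |
|---|---|---|---|---|
| 90 | 2 | 2.88 | 2.91 | 1.1% |
| 90 | 4 | 2.77 | 2.83 | 2.2% |
| 90 | 7 | 2.60 | 2.70 | 3.9% |
| 60 | 2 | 2.28 | 2.33 | 2.1% |
| 60 | 4 | 2.17 | 2.26 | 4.3% |
| 60 | 7 | 2.00 | 2.16 | 7.6% |

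**Step 4: whole trial, 90-day follow-up.** At 2300 there are about 766.7 controls and 1533.3 LifeVest participants. Expected events at the design rates are 766.7 × 3.0% + 1533.3 × 1.02% = 23.0 + 15.6 = 38.6, about 39. At g = 7 the control loss per participant is F(97) − F(90) = 0.1055 percentage points, and 0.34 of that with the LifeVest.
- Everyone at day 7 (the ceiling): 766.7 × 0.1055% + 1533.3 × 0.34 × 0.1055% = 0.81 + 0.55 = 1.36, about 1.4 events.
- 50% at day 7: 0.7 events.
- 25% at day 7: 0.3 events.

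**Cross-check without the curve.** The average month-3 risk is (3.0 − 2.4)/30 = 0.02 points per day. Seven lost days remove 0.14 points, taking 3.0% to 2.86%. The ceiling is then 766.7 × 0.14% + 1533.3 × 0.34 × 0.14% = 1.1 + 0.7 = 1.8 events, the same order.

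**The case against.** The strongest reply is that this is housekeeping.
- The SAP (v1.3, March 2017) is later than protocol v3.2 (June 2016) and already has a sound rule. Its change log shows it replacing the exact stratified primary test of 1.5.11 with a chi-square test, so it looks like the current analysis plan.
- Aim 1 places randomization at hospital discharge, and the exclusion in 1.5.11 is worded for people randomized in hospital. The sentence was probably drafted with them in mind, and for them the rules coincide.
- The expected loss is below one event unless late enrollment was very common.

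Most of this stands, and it limits the weight of the point. It does not remove the conflict. The SAP log records no change to the modified-ITT start date, no text gives the SAP precedence, and section 2.6 still points to 1.5.11. For total mortality and the other secondary outcomes, the protocol rule is the only modified-ITT clock stated.

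A reader might infer more than the documents support:
- **That event-free time favours one arm.** The gap ends at randomization, so it can differ between arms only by chance, and the proportional loss should be similar in both.
- **That the documents give two conflicting total-mortality counts.** Only the protocol puts total mortality through this analysis, so there is one stated rule for it, with the same flaw.
- **That the primary result is affected.** Both documents run the primary analysis from randomization.

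**Conclusion.** The inconsistency is in current text, and for post-discharge enrollees the protocol's version miscounts as written. Its effect is small: at most about 1.4 of about 39 expected primary events with 90-day follow-up, and well under one event if a quarter or fewer were randomized as late as day 7. For an individual late enrollee the shortfall is larger with 60-day follow-up (up to 7.6%) than with 90-day (up to 3.9%).

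These sizes rest on the exponential shape, time zero at discharge, the design rates, a constant ratio of 0.34 between arms, and an assumed share of late enrollees. The existence of the discrepancy rests on none of them. This is a minor wording correction to a secondary analysis.

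**What to change.** Replace the sentence in protocol 1.5.11 with the SAP rule: modified-ITT follow-up begins at the later of randomization or discharge and ends 60/90 days after that date. State that this applies to every outcome analysed by modified ITT, including total mortality.

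A statement that the SAP governs would settle the primary outcome, but not the outcomes that only the protocol assigns to this analysis.

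The cost is one sentence. No new data are needed: for a participant already discharged at randomization, the SAP window is the same as the primary ITT window.
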